2.5.5 Unscheduled visits

Unscheduled visit measurements of laboratory data, vital signs, and ECG but will be used for computation of baseline, the last on-treatment value, PCSAs, and the shift summaries for safety or efficacy. They will be included in the by-visit summaries if they are re-allocated to scheduled visits (see [Section 2.5.4](#)).

2.5.6 Pooling of centers for statistical analyses

Center will not be included in the statistical models for efficacy analyses. However, all centers within a country will be pooled, and country will be included as a fixed effect in a parametric statistical model (eg, ANCOVA etc) for primary and secondary efficacy endpoints. Countries with fewer than 5 randomized patients will be grouped, if patients from grouped countries are still fewer than 5, they will then be further grouped with the country with the lowest number of patients that is 5 or more.

2.5.7 Statistical technical issues

None.

3 INTERIM ANALYSIS

No formal interim analysis for efficacy is planned since analysis of primary and secondary efficacy endpoints will be considered final at the time of first step analyses described below. The study analyses will be conducted in 2 steps.

- First step: Efficacy analyses up to Week 26 and interim safety analyses

The first step analyses will be conducted when all patients have been randomized and have their data at the minimum up to Week 26 collected and validated. For this analysis the common cut-off date is 15 days after the date of last patient last Week 26 visit. The first step analyses will include:

- Efficacy analyses up to Week 26, which are considered as the final analyses for primary and secondary efficacy endpoints. The analyses beyond 26-week will be descriptive.
- Interim safety analyses which will be performed on all safety data collected and validated at the time of the first step analyses.

The first step analyses will not be used to change the conduct of the ongoing study in any aspect. Since the primary and secondary efficacy analyses would have been concluded at the time of the first step analyses, the significance level for the study remains at 0.05 (see [Section 2.4.4.2](#)). The first step analyses will be included in the submission dossier to health authorities.

- Second step: Final analyses

The second step analyses will be conducted at the end of the study. The second step analyses will include the final analyses of efficacy endpoints at Week 52 and safety endpoints, which will be descriptive only.

Individuals who are involved in the unblinding of the first step analysis will not be involved in the conduct of the study afterwards.

Analyses methods and conventions described in the other sections of this SAP will be applied for all analyses as applicable. The following additional rules will be applied for analyses performed at first step analysis:

- Any assessments within analysis windows up to Week 26 will be taken into account (may include few unscheduled data after the cut-off date).
- Patients without end of treatment visit performed at the time of the cut-off date will be considered as ongoing and exposed up to the cut-off date. Therefore:
 - Patients who did not complete 52-Week entire treatment period nor prematurely discontinued the study treatment at cut-off date will be analyzed as “ongoing” in the disposition summary;
 - Their TEAE period, and on-study observation period will end at the cut-off date;

Statistical Analysis Plan

Version: Final 3.0

Lexicon Pharmaceuticals Protocol No. EFC15166

Date of Issue: 21 November 2019

Covance Study ID: 000000155203

- Their treatment duration will be derived by considering date of cut-off as last administration date.
- Analyses of percentage of days with under/above-planned dosing and compliance will be performed before the last administration reported in the e-CRF up to the last visit before cut-off date.
- AEs occurring, worsening or becoming serious after the cut-off date will not be included in the analyses. However, any available outcome before database lock, regardless of timing in relation to the cut-off date, of an adverse event starting prior to the cut-off date will be taken into account. Medications, treatment discontinuations/completions, and deaths occurring after the cut-off date will not be included in the analyses.
- For time to severe or documented symptomatic hypoglycemia at the 1st step analysis, the censoring date is min (EOT+1, EOS, common cut-off date).
- Post-treatment period, post-study period are not applicable for ongoing patients. Analyses of post-treatment AEs, post-study deaths, and post-treatment medications will be performed for patients who either completed or prematurely discontinued the treatment before or at the cut-off date.
- Status at last study contact will be provided for patients who either completed or prematurely discontinued the study before or at the cut-off date.

An independent Data Monitoring Committee (DMC) will be used to monitor and assess the safety of patients from this trial through periodic review of the accumulated safety data provided by an independent statistical group. Related details are provided in separate documents (DMC charter and DMC SAP).

4 DATABASE LOCK

Two database locks will be done:

- First database lock (for first step analysis): will include all available data on all randomized patients up to the common cut-off date as defined in Section 3. This database lock is planned to be done approximately 4 weeks after the common cut-off date.
- Final database lock (for second step analysis): will include all data, including follow-up, for all randomized patients. This database lock is planned to be done approximately 4 weeks after last patient last visit.

5 SOFTWARE DOCUMENTATION

All summaries and statistical analyses will be generated using SAS[®] version 9.2 or higher.

Appendix A Sample SAS® code for analyses of efficacy endpoints

```

* VARIABLES;
* ptid - patient identification;
* treat - treatment;
* strata1 - stratification factor 1;
* strata2 - stratification factor 2;
* value0 - value at baseline;
* value1 ... valuen - value at each post-baseline visit for a total of n visits; valuen at the endpoint visit;
* change - change from baseline;

***** Part 1: Preferred imputation method: the retrieved dropouts and washout imputation *****,;
*****
*.;

/* Part 1a, for parameters with no missing data at baseline */;

* MI in patients who prematurely discontinued IMP before the endpoint using the endpoint data from its
own group (retrieved dropouts);
proc sort data=ads;
  by treat ptid;
run;

proc mi data=ads out=disc_mi nimpute=2000 seed=97531;
  where discontinue = "Y";
  by treat;
  var value0 valuen;
  monotone regression (valuen = value0 );
run;

* MI in patients who stay on the IMP until the endpoint visit using the endpoint data from the placebo group
(wash-out MI);
proc sort data=ads;
  by ptid;
run;

proc mi data=ads out=comp_mi nimpute=2000 seed=75319;
  where discontinue="N" and (treat=1 or (treat ne 1 and valuen =. )); *1 denotes placebo group;
  class strata1 strata2;
  var strata1 strata2 value0 valuen;
  monotone regression (valuen = strata1 strata2 value0 );
run;

* Repeat dataset with the same number of replications for remaining patients who have complete data at
the endpoint visit;
data comp_trt;

```

Statistical Analysis Plan

Version: Final 3.0

Lexicon Pharmaceuticals Protocol No. EFC15166

Date of Issue: 21 November 2019

Covance Study ID: 000000155203

```
set ads (where=(discontinue="N" and treat ne 1 and valuen ne .));
_imputation_=0;
do i = 1 to 2000;
    _imputation_=_imputation_+1;
    output;
end;
run;
```

* Combine MI from the three subsets of patients;

```
data mi_1;
    set disc_mi comp_mi comp_trt;
run;
```

/*Part 1b, for parameters with missing data at baseline */

* To impute the missing data at baseline;

```
proc sort data=ads;
    by ptid;
run;
```

```
proc mi data=ads out=mi_base nimpute=2000 seed=13579;
    class strata1 strata2;
    var strata1 strata2 value0;
    monotone regression;
run;
```

* MI in patients who prematurely discontinued IMP before the endpoint using the endpoint data from its own group (retrieved dropouts);

```
proc sort data=mi_base;
    by _imputation_ treat ptid;
run;
```

```
proc mi data=mi_base out=disc_mi nimpute=1 seed=97531;
    where discontinue = "Y";
    by _imputation_ treat ;
    var value0 valuen;
    monotone regression (valuen = value0 );
run;
```

* MI in patients who stay on the IMP until the endpoint visit using the endpoint data from the placebo group (wash-out MI);

```
proc sort data=mi_base;
    by _imputation_ ptid;
run;
```

```
proc mi data= mi_base out=comp_mi nimpute=1 seed=75319;
```

Statistical Analysis Plan

Version: Final 3.0

Lexicon Pharmaceuticals Protocol No. EFC15166

Date of Issue: 21 November 2019

Covance Study ID: 000000155203

```
where discontinue="N" and (treat=1 or (treat ne 1 and valuen =. )); *1 denotes control group;
by _imputation_;
class strata1 strata2;
var strata1 strata2 value0 valuen;
monotone regression (valuen = strata1 strata2 value0 );
run;

* Combine datasets;
data mi_1;
    set disc_mi comp_mi mi_base (where=( discontinue="N" and treat ne 1 and valuen ^=.));
run;
```

```
*****.
*****Part 2: Backup imputation method : Control-based copy reference multiple imputations
*****.
*****.
```

/* Data preparation */;

/*For categorical variables with more than 2 levels, dummy binary variables have to be created before using SAS procedure to generate monotone missing data since MCMC method does not take categorical variables */;

/*Below using a treatment group of 3 levels as an example*/;

```
data ads1;
    set ads0 (keep=ptid treat);
run;
```

* Output dataset ADS1 contains the original variable TREAT & dummy variables TREAT1, TREAT2;

```
proc transreg data=ads1 design;
    model class (treat / zero= last); * proper sorting needed to ensure correct reference group;
    output out=ads2 (drop=_type__name_ intercept);
    id ptid;
run;
```

```
data ads;
    merge ads0 ads2;
    by ptid;
run;
```

/*Part 2a, for parameters with no missing data at baseline*/;

* Partial imputations to render monotone missing data;

```
proc sort data=ads;
    by treat1 treat2 strata1 strata2 strata3 ptid;
```

Run;

```
proc mi data=ads out=monotone nimpute=2000 seed=97531;
```

Statistical Analysis Plan

Version: Final 3.0

Lexicon Pharmaceuticals Protocol No. EFC15166

Date of Issue: 21 November 2019

Covance Study ID: 000000155203

```
by treat1 treat2 strata1 strata2 ;
var value;;
mcmc chain=multiple impute=monotone;
run;

* Partial imputations to render monotone missing data; Drop strata if not converge;
proc sort data=ads;
  by treat1 treat2 ptid;
Run;

proc mi data=ads out=monotone nimpute=2000 seed=97531;
  by treat1 treat2;
  var value;;
  mcmc chain=multiple impute=monotone;
run;

* To impute the missing data at post-baseline visits;
proc sort data= monotone;
  by _imputation_ ptid;
run;

proc mi data= monotone out=mi_1 nimpute=1 seed=75319;
  by _imputation_;
  class treat strata1 strata2;
  monotone reg ( / details);
  mnar model (value: / modelobs=(treat='1')); *1 denotes placebo group;
  var strata1 strata2 value;;
run;

/*Part 2b, for parameters with missing data at baseline */
* To impute the missing data at baseline;
proc sort data=ads;
  by ptid;
run;

proc mi data=ads out=mi_base nimpute=2000 seed=13579;
  class strata1 strata2;
  var strata1 strata2 value0;
  monotone regression;
run;

* Partial imputation to render monotone missing;
proc sort data=ads;
```

```
by _imputation_ treat1 treat2 strata1 strata2 ptid;
Run;
```

```
proc mi data=ads out=monotone nimpute=1 seed=97531;
  by _imputation_ treat1 treat2 strata1 strata2 ;
  var value;;
  mcmc chain=multiple impute=monotone;
run;
```

* Partial imputations to render monotone missing data; see Part 2a for dropping strata if not converge;

```
* To impute the missing data at post-baseline visits;
proc sort data= monotone;
  by _imputation_ ptid;
run;
```

```
proc mi data=monotone out=mi_1 nimpute=1 seed=57913;
  by _imputation_ ;
  class treat strata1 strata2;
  monotone reg ( / details);
  mnar model (value: / modelobs=(treat='1')); *1 denotes placebo group;
  var strata1 strata2 value;;
run;
```

```
*****

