1.6 STATISTICAL MODIFICATIONS MADE IN THE STATISTICAL ANALYSIS PLAN

The statistical analysis plan history table below gives the timing, rationale, and key details for major changes to the statistical analysis features in the statistical analysis plan. Changes also incorporated in a protocol amendment are cross-referenced to [Table 1](#).

Statistical Analysis Plan

Version: Final 3.0
Lexicon Pharmaceuticals Protocol No. EFC15166

Date of Issue: 21 November 2019
Covance Study ID: 000000155203

[figure not shown]
[figure not shown]
Table 2 - Statistical analysis plan statistical changes

SAP version number	Date approved	Rationale	Description of statistical changes
1	04-Oct-2018	Urgent coronary revascularization not adjudicated by CEC to be consistent with outcome trials	Urgent coronary revascularization not included in adjudication related analyses*.
1	04-Oct-2018	5 half-lives of sotagliflozin prolonged to 15 days considering patients with severe renal dysfunction	5 half-lives of IMP updated from 5 days to 15 days; TEAE period updated accordingly*
1	04-Oct-2018	Baseline eGFR defined as recommended by CDISC Therapeutic Area Data Standards User Guide for Diabetic Kidney Disease	For serum creatinine and eGFR, the baseline value is defined as the average of all values before the first dose of double-blind IMP for those randomized and exposed or before randomization for those who were randomized but never exposed to IMP*.
1	04-Oct-2018	The effect in body weight is considered more closely associated with the planned indication.	Change in the order of secondary objectives and endpoints for the study
1	04-Oct-2018	Clarification on EOSI renal events	Details specified on renal events to be consistent with outcome studies in Section 2.1.4.2 .
1	04-Oct-2018	Clarification on ESRD	ESRD is defined in Section 2.4.4.3 consistent with CEC charter.
1	04-Oct-2018	[REDACTED]	[REDACTED]
1	04-Oct-2018	[REDACTED]	[REDACTED]
1	04-Oct-2018	Updating the wording to be consistency with CEC charter	"Unstable angina leading to hospitalization" changed to "Unstable angina requiring hospitalization"
2	05-Jun-2019	[REDACTED]	[REDACTED]
2	05-Jun-2019	Number of iterations for multiple imputation was changed	Number of iterations for multiple imputation was changed from 10000 to 2000
2	05-Jun-2019	Wording change to be consistent with CEC charter	"Heart failure leading to hospitalization" changed to "Heart failure requiring hospitalization"

Statistical Analysis Plan

Version: Final 3.0

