2.4.4.2 Analyses of secondary efficacy endpoints

For continuous secondary efficacy parameters (see [Section 2.1.3](#)) with missing data at baseline, missing data will be imputed using MI under the missing at random (MAR) assumption. Missing data at baseline will be imputed using regression method that includes randomization stratum of HbA1c ($\leq 8.5\%$, $> 8.5\%$), randomization stratum of SBP (< 130 , ≥ 130 mmHg), and baseline value in the imputation model (see sample code Part 1 or 2b in [Appendix A](#)).

Each continuous secondary endpoints (see [Section 2.1.3](#)) will be analyzed using a similar ANCOVA model including the measurements at baseline and endpoint (observed or imputed). The missing data at endpoint will be imputed by the retrieved dropouts & washout imputation method or by the control-based copy reference imputation method according to the criterion described in [Section 2.4.4.1](#). After the imputation, each of the complete datasets will be analyzed by an ANCOVA model.

The ANCOVA model with treatment groups (sotagliflozin 400 mg, sotagliflozin 200 mg, placebo), randomization stratum of HbA1c ($\leq 8.5\%$, $> 8.5\%$), randomization stratum of SBP (< 130 , ≥ 130 mmHg), and country as fixed effects, and baseline secondary endpoint value as a covariate. For the analysis of SBP in patients with baseline SBP ≥ 130 mmHg, the randomization stratum of SBP will not be included in the ANCOVA model. Results from each complete dataset will be combined using Rubin's rule to provide the adjusted mean change from baseline to Week 26 (or Week 12 for SBP) for each treatment group, as well as the between-group difference (comparing sotagliflozin 400 mg, sotagliflozin 200 mg vs placebo) and the 95% CI for the difference.

UACR will be log-transformed at patient level before analysis, and geometric means (with and without ANCOVA model adjustment), differences between treatments and 95% CIs will be back-transformed to original scale. Summary statistics of UACR in log scale will then be calculated for

each treatment group at each visit and back-transformed to provide the geometric mean and its associated percent change of UACR from baseline.

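### SAP Appendix A Part 2b imputes missing baselines and then never uses them: the next step reads the wrong dataset and cannot run as printed

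*SAP*

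**What the plan says.** SAP 2.4.4.2 states that, for continuous secondary endpoints with a missing baseline, "missing data will be imputed using MI under the missing at random (MAR) assumption". The model is a regression on the randomization strata: "Missing data at baseline will be imputed using regression method that includes randomization stratum of HbA1c" and the SBP stratum. For the implementation it refers the reader to the appendix: "see sample code Part 1 or 2b in" Appendix A. Part 1 serves the preferred method (retrieved dropouts and washout). Part 2b serves the back-up method (control-based copy reference), which SAP 2.4.4.1 triggers when any arm has fewer than 5 retrieved dropouts.

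The number of imputations is in SAP 1.6, Table 2: "Number of iterations for multiple imputation was changed from 10000 to 2000". The table says iterations, but the code shows that `nimpute` is meant.

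Part 2b has three steps:

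1. Baseline imputation: "proc mi data=ads out=mi_base nimpute=2000 seed=13579".
2. A sort of `ads` "by _imputation_ treat1 treat2 strata1 strata2 ptid", then the partial imputation to a monotone pattern: "proc mi data=ads out=monotone nimpute=1 seed=97531", also BY `_imputation_`.
3. The control-based step for post-baseline visits: "proc mi data=monotone out=mi_1 nimpute=1 seed=57913".

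**The concern.** Step 2 should take up the 2000 copies that step 1 wrote. It returns to the dataset that existed before step 1. The imputed baselines therefore go nowhere, and the sort and the BY statement call for a variable that is not there.

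At stake is whether the code cited for the back-up analysis carries out the method in 2.4.4.2. An error message will be noticed. The risk lies in how it is then repaired, because two natural repairs make the code run without restoring the stated method.

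**Working it through.** This is a trace of the listing; SAS itself was not run.

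**Does `ads` carry `_imputation_`?** In the data preparation for Part 2, `ads` is a merge of `ads0` with the treatment dummy variables in `ads2`. Neither step creates `_imputation_`, and the variable list that opens Appendix A does not include it. PROC MI adds it to its output, so after step 1 it is on `mi_base` only.

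**How many completed datasets does each listing give?** The rule is

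completed datasets = (distinct `_imputation_` values in the input, or 1 if none) × `nimpute`.

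| Listing | Input to the imputation step | Count |
|---|---|---|
| Part 1a | `ads`, no BY `_imputation_`, `nimpute=2000` | 1 × 2000 = 2000 |
| Part 1b | `mi_base`, BY `_imputation_`, `nimpute=1` | 2000 × 1 = 2000 |
| Part 2a | `ads`, no BY `_imputation_`, `nimpute=2000`; then `nimpute=1` | 1 × 2000 × 1 = 2000 |
| Part 2b as printed | `ads`, BY `_imputation_`, `nimpute=1` | none: BY variable absent |
| Part 2b, `_imputation_` dropped from BY | `ads`, `nimpute=1`; then `nimpute=1` | 1 × 1 × 1 = 1 |
| Part 2b, copied from Part 2a | `ads`, `nimpute=2000`; then `nimpute=1` | 1 × 2000 × 1 = 2000, `mi_base` unused |
| Part 2b reading `mi_base` | `mi_base`, BY `_imputation_`, `nimpute=1`; then `nimpute=1` | 2000 × 1 × 1 = 2000 |

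Parts 1a, 1b and 2a reproduce the 2000 in Table 2. Part 2b mixes two patterns: the input of Part 2a with the BY statement and `nimpute` of Part 1b.

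**What the two unsound repairs do.**

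- *Drop `_imputation_` from BY.* PROC MI then writes its own `_imputation_` = 1, so step 3 runs, with one completed dataset. Rubin's total variance is T = U + (1 + 1/m)B, where B has divisor m − 1. At m = 1 the divisor is 0, so B and T are undefined.
- *Copy Part 2a.* The count is right, but the baselines from step 1 are still ignored.

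Under either repair, a baseline that is missing while later visits are observed is filled by the MCMC monotone step, within arm (and stratum, unless dropped) and using post-baseline values. That is not the strata-based MAR regression of 2.4.4.2.

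**Which endpoints can reach Part 2b?** Two conditions must both hold: a missing baseline, and routing to the back-up method. Baseline is the last available pre-dose value, unscheduled values included (SAP 2.1.1 and 2.5.4). By the flow chart in Protocol 1.2:

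- SBP and body weight are measured at Visits 1, 2 and 3, and HbA1c and FPG at Visits 1 and 3. A missing baseline should be rare.
- Home urine is first collected at Week 0, so UACR has no earlier scheduled value to fall back on.

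**The case against.** The strongest case against is that this is a slip in code headed as a sample. The prose in 2.4.4.2 is not wrong, the method it describes can be programmed, and a step that fails yields no misleading result. All of that stands. It does not dispose of the point, because 2.4.4.2 cites Part 2b as the implementation. Its prose also lists the baseline value itself among the variables of the model that imputes missing baselines, so a programmer will look to the code to see what predicts what.

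A reader might infer more than the documents support, in four ways:

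- *That confidence intervals would be too narrow.* This needs a particular faulty repair, and the specified pooling (Appendix A Part 5) would then break down at m = 1. A narrow pooled interval would also require abandoning that step.
- *That Week 12 SBP is exposed.* SBP may well trigger the back-up method, but with pre-randomization values available it would normally use Part 2a, which does not have this fault.
- *That the tested hierarchy is affected through UACR.* The UACR tests in SAP 2.4.4.4 are limited to patients with baseline UACR above 30 mg/g. A patient without an observed baseline cannot be placed in that subset on observed data, and the SAP does not say that imputed baselines define it. The all-patients UACR analysis in Appendix D is more exposed, but it is outside the hierarchy. Flow-chart footnote p also asks for the visit to be rescheduled if a urine collection is missed.
- *That `nimpute=1` is the error.* Raising it to 2000 while still reading `ads` would not bring the imputed baselines back.

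**Conclusion.** Part 2b is wrong as written. It cannot run, it leaves the 2000 imputed baselines unused, and it does not implement the method that cites it. The practical reach is small: realistically UACR, mainly the all-patients analysis, and only if some baselines are missing and an arm has fewer than 5 retrieved dropouts for that endpoint. SAP 1.6 repeats the secondary analyses at Week 52, so the same code could be used again there.

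No effect on an estimate or standard error can be given. The documents state neither the number of missing baselines nor the number of retrieved dropouts, and any percentage would rest on an assumed fraction of missing information. The conclusion assumes that `ads` is built as Appendix A shows, without `_imputation_`.

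**What to change.** In Part 2b, replace `ads` with `mi_base` in the second PROC SORT and in the partial-imputation PROC MI. Keep BY `_imputation_` and `nimpute=1`, as Part 1b does. Add to the comment that sends the reader to Part 2a for dropping strata that, here, the fallback also starts from `mi_base`, BY `_imputation_` and the treatment dummies, with `nimpute=1`.

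The cost is two dataset names and one line of comment. The stated method, endpoints and testing order do not change. Because SAP 1.6 says the first-step analysis has already been run for top-line results, the CSR should state which code was used for any endpoint that went through Part 2b.
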